6. STUDY INTERVENTION

Study intervention is defined as any investigational intervention(s), marketed product(s), placebo, or medical device(s) intended to be administered to a study patient according to the study protocol.

6.1. Study Intervention Administered

Table 5 presents a summary of the study interventions administered for each of the treatment arms. Details regarding study intervention administration are described in Section 6.1.1 through Section 6.1.4.

Table 5: Study Interventions Administered

Group	1 (Arm A)	1 (Arm B) ^a	2 ^b	Safety Lead-in (Cohorts I and II) and Cohorts III-V
Arm Name	A	В	NA	NA
Intervention	MT-401	SoC	MT-401	MT-401
Name		(Observation)		
Type	Investigational	NA	Investigational	Investigational Product
	Product		Product	
Dose	Multi-antigen	NA	Multi-antigen	Multi-antigen specific
Formulation	specific CD4 ⁺ and		specific CD4 ⁺ and	CD4 ⁺ and CD8 [‡] T cells
	CD8 ⁺ T cells		CD8 ⁺ T cells	
Unit Dose	100 x 10 ⁶ cells flat	NA	100 x 10 ⁶ cells flat	Sa fety Lead-in
Strength ^c	dose		dose	(Cohorts I & II):
				50 x 10 ⁶ cells flat dose
	$(or 200 \times 10^6 cells)$		$(or 200 \times 10^6 cells)$	
	flat dose as		flat dose as	

Confidential Page 37 of 74

Group	1 (Arm A)	1 (Arm B) ^a	2 ^b	Safety Lead-in (Cohorts I and II) and Cohorts III-V
Arm Name	A	В	NA	NA
	determined by Sponsor)		determined by Sponsor)	Cohort III: 200 x 10 ⁶ cells flat dose
				Cohort IV: 100 x 10 ⁶ cells flat dose
				Cohort V: 200 x 10 ⁶ cells flat dose
Dosage Level ^d	Up to 3 doses total, with each dose at least 2 weeks apart	NA	Up to 3 doses total, with each dose at least 2 weeks a part	Up to 3 doses total, with each dose at least 2 weeks apart
Route of Administration	IV infusion through either a peripheral or a central line	NA	IV infusion through either a peripheral or a central line	IV infusion through either a peripheral or a central line
Use	Experimental	Comparator	Experimental	Experimental
Sourcing	Provided centrally by the Sponsor	Locally by the study site, subsidiary, or designee.	Provided centrally by the Sponsor	Provided centrally by the Sponsor

Abbreviations: AE=adverse event; HSCT=hematopoietic stem cell transplant; IV=intravenous; NA=not applicable; SoC=standard of care ^a Patients in Group 1 – Arm B who relapse after randomization may cross over to Group 2 to receive MT-401, if the subgroup is open and/or Sponsor agreement.

6.1.1. Pre-Medication

Patients are recommended to be pre-medicated before MT-401 with diphenhydramine (Benadryl) up to 1 mg/kg IV (max 50 mg) and acetaminophen (Tylenol) up to 10 mg/kg orally (max 650 mg), and/or as per institutional guidelines.

6.1.2. Cell Administration

MT-401 will be given by IV infusion through either a peripheral or central line. Further details are provided in the Investigational Product Manual.

6.1.3. Monitoring of Infusion

Monitoring will be undertaken according to institutional standards for administration of blood products with the exception that the infusion will be given by a physician or trained professional. The patients will be monitored for any safety concerns for 1 hour post-infusion as outpatients.

Confidential Page 38 of 74

b If relapse occurs less than 80 days post-HSCT and T cells have been manufactured and stored, the patient may receive T cells and be included in a subgroup analysis of Group 2 (study intervention details for the subgroup will be the same as those presented for Group 2 in the table).

^c Manufacturing maximum will also dictate the dose. As a result, patients may receive doses different to those listed; these patients will complete the study but will be unevaluable.

^d Timing of MT-401 administration (at least every 2 weeks) may be modified for 1 week due to inclement weather, vacation, etc., but any longer durations need to be discussed with the Sponsor. Administration of MT-401 can be delayed due to management of AEs or other toxicities, but patients should resume T cell infusions within 2 weeks of their scheduled dose. If greater than 2 weeks is needed, Sponsor will determine if patient can resume T cells infusions.

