6.6. Dose Modification

No dose modifications will be allowed except in rare instances of manufacturing constraints, and any other issues specifically discussed with the Sponsor. As a result, patients may receive either lower or higher than the intended doses; these patients will complete the study but will be evaluable in a separate sub-group.

Timing of MT-401 administration (at least 2 weeks apart) may be modified for 1 week due to inclement weather, vacation, etc., but any longer durations need to be discussed with the Sponsor. Administration of MT-401 can also be delayed due to management of AEs or other toxicities, but patients should resume T cell infusions within 2 weeks of their scheduled dose. If greater than 2 weeks is needed, Sponsor will determine if patient can resume T cells infusions. All dose modifications should be documented, including the approach taken and a clear rationale for the need for modification. Additionally, the investigator must assess if a toxicity is considered attributable to T cells. If MT-401 is available for a patient, a patient may be re-dosed if requested by the investigator and approved by the Sponsor on a case-by-case basis.

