9.2. Populations for Analyses

Populations for analyses are defined in Table 8.

Table 8. Populations for Analysis

Population	Description
All enrolled patients	All patients who sign the ICF and donor undergoes leukapheresis
All randomized patients in Phase 2 (Adjuvant - Group 1 only)	All patients in Group 1 who are randomized with final dose and manufacturing process, and are MRD prior to randomization by central testing and local testing (if a local test was a lso performed). Efficacy analyses for Group 1 will be conducted in this population. A patient randomized based on negative MRD result per central test but confirmed to be MRD will be excluded from Group 1 analyses. The patient will
All treated patients	be included in Group 2 Subgroup D analyses if treated with MT-401. All patients who receive at least one dose of MT-401 or were randomized to SoC. Patients whose product includes fewer cells or does not meet specifications may still be treated, but will be summarized separately from patients whose product meets specifications. For - Group 1, safety analyses will be conducted in this population, and safety data for patients randomized to SoC will also be shown for reference. For - Group 2, all efficacy analyses and safety analyses will be conducted in this population. For the Safety Lead-in (Cohorts I and II) and Cohorts III-V, all efficacy and safety analyses will be conducted in this population.
DLT-eva luable	All patients in the Safety Lead-in (Cohorts I and II) and Cohorts III-V who receive at least one dose of MT-401 and have had the opportunity to be followed for 28 days from the initial MT-401 infusion or have experienced a DLT.
Per-protocol in Phase 2	All treated patients, as defined above, who have no major protocol deviations. Select efficacy analyses for Group 1 and Group 2 will be conducted in this population for sensitivity analysis.

Confidential Page 51 of 74

Abbreviations: DLT=dose-limiting toxicity; ICF=informed consent form; MRD=minimal residual disease; SoC=standard of care

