assessments	assessment prior to the missed disease	
	assessments	

Abbreviations: AML=acute myeloid leukemia; RFS=relapse-free survival

RFS curves will be estimated using the Kaplan-Meier (KM) product limit method. For Group 1, the hazard ratio and corresponding 95% confidence interval (CI) will be estimated using a Cox proportional hazards model using randomized arm and two stratification factors as covariates. The KM estimate of the medians will be reported, and the corresponding 95% CI will be computed. KM estimates of RFS rates at milestone time points will be reported along with two-sided 95% CIs using Greenwood's formula, provided the minimum follow-up in patients exceeds the time point to support stable estimation of the rate. In addition to the Cox model, a stratified log-rank test will be used to compare the treatment arms, stratified by pre-transplant MRD status (MRD+ vs. MRD-/Unknown) and cytogenetic risk (Unfavorable vs. Other).

RFS is defined as the time between the date of first dose and the date of first relapse per ELN recommendations or death by any cause for Group 2 patients, and will be summarized for Group 2 Subgroup D patients and those in Group 2 who are in CR_{MRD} prior to administration of MT-401.

9.3.3. Primary Efficacy Analysis: Group 2

The primary endpoints for Group 2 are CR rate and duration of complete response. For Group 2 Subgroup C, CR rate is defined as the proportion of treated patients who achieve a best response of CR_{MRD} - or CR using the ELN recommendations. For Group 2 Subgroup D, CR rate is defined as the proportion of treated patients who achieve a best response of CR_{MRD} -. Best overall response (BOR) is defined as the best response designation recorded between the date of first dose and the date of objectively documented progression or relapse per ELN recommendations or the date of subsequent therapy, whichever occurs first. For patients without documented progression or subsequent therapy, all available response designations will contribute to the BOR assessment.

The primary analysis will occur after all patients treated have been followed for 6 months.

For Group 2 Subgroup C, duration of complete response is defined as the time between the date of first documented response of CR_{MRD}- or CR to the date of the first documented relapse per ELN recommendations or death due to any cause, whichever occurs first. For Group 2 Subgroup D, duration of

Confidential Page 53 of 74

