7.2 Analysis Populations

The analysis populations are defined as follows:

- All Treated Patients: Includes all patients who received at least one dose of MT-401 or were randomized to SOC.
- All Randomized Patients: Includes all patients in Group 1 who were randomized with final dose and manufacturing process and are MRD⁻ prior to randomization by central testing and local testing, if a local test was also performed. A patient randomized based on negative MRD result per central test but confirmed to be MRD⁺ will be excluded from Group 1 analysis.

When MRD testing occurs with different methodology (eg, flow cytometry and PCR), the patient is considered MRD⁺ if either test detects MRD. If adjudication occurs between central testing and local testing for the same type of testing (eg, flow by central testing and flow by local testing), the final adjudicated result will be taken into account for the confirmed MRD result. A patient confirmed to be MRD⁺ prior to randomization will be excluded from Group 1 and will be included in Group 2 analysis if treated with MT-401.

- Per-Protocol (PP) Population: Includes all treated patients, as defined above, who have no major protocol deviations. If there is <5% difference in the all randomized patient population and the PP population for Group 1, no analyses will be performed on the PP population.

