7.4 Efficacy Evaluation

7.4.1 *Datasets Analyzed*

Efficacy analyses for Group 1 will be conducted in the all randomized patients population while efficacy analyses for Cohorts I-V and Group 2 will be conducted in the all treated patients population. Select efficacy analyses for Group 1 will be repeated in the PP population. A data listing of patients excluded from the PP Population, to include the reason for exclusion, will be presented.

7.4.2 *Demographic and Other Baseline Characteristics*

Demographic and baseline characteristics will include: age, sex, ethnicity, race, height, weight, and body mass index (BMI). Age will be calculated relative to date of informed consent, as follows:

- If the month and day portion of the informed consent date is prior to the month and day portion of the birthdate, age will be calculated as the year of informed consent minus the year of birth, minus one;
- If the month and day portion of the informed consent date is on or after the month and day portion of the birthdate, age will be calculated as the year of informed consent minus the year of birth.

BMI will be calculated as: weight (kg) / [height (cm) / 100]². Age, height, weight, and BMI will be summarized using descriptive statistics. Sex, age category (18-64 years, 65 years and above), ethnicity, and race will be summarized with the number and percentage of patients in each parameter category.

Disease history characteristics include: time since initial diagnosis (months), WHO classification, type of AML (secondary or treatment-related AML, de novo AML), disease status at screening, disease status at baseline, bone marrow blast percentage at baseline (for Cohort I-V and Group 2) complete remission prior to transplant (CR1/CR2/CR3; for Group 1 only), prior stem cell transplant (yes/no), time from transplant to randomization/first dose, time from first post-transplant relapse to first dose (for Cohort I-V and Group 2), history of post-transplant chronic GVHD (yes/no), maximum grade of chronic GVHD, history of post-transplant acute GVHD (yes/no), maximum grade of acute GVHD, type of transplant donor, conditioning regimen, MRD status pre- and post-transplant, genetic mutations identified, disease risk classification (favorable,

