The primary endpoint of RFS for Group 1 will be tested at $\alpha = 0.05$ (two-sided) at the final analysis. The analysis of RFS at the interim analysis will be performed for the purposes of testing for futility and possible re-estimation of sample size as described in [Section 7.4.7.3](#). Analysis at the interim and final analysis will be performed based on ([Chen et al. 2004](#)) in order to maintain the type 1 error at $\alpha = 0.05$ for RFS at the final analysis.

Secondary endpoints for Group 1, OS and GRFS, will be presented for descriptive purposes only and no adjustments will be made for multiplicity.

The primary endpoint of CR for Group 2 will be tested at $\alpha = 0.05$ (two-sided) at the final analysis. DOCR will be presented for descriptive purposes only and no adjustments will be made for multiplicity.

7.4.7.6 *Use of an “Efficacy Subset” of Patients*

The primary efficacy analysis for Group 1 will be performed on all randomized patients and the PP population will be utilized as a sensitivity analysis. The PP population will exclude patients received less than two-thirds of total planned dose or had other major protocol deviations.

7.4.7.7 *Examination of Subgroups*

Subgroup analyses may be conducted based on, but not limited to, the covariates defined in [Section 7.4.7.1](#).

For time to event endpoints forest plots of the event-free rates at landmark times may be generated to display the outcomes in subgroups. Additionally, Kaplan-Meier plots with subgroup KM curves overlaid on the same plot may be presented. For binary endpoints, the rates within subgroups may be presented in forest plots.

7.5 **Safety Evaluation**

Safety analysis will be carried out for the all treated patients population, to include all patients who receive at least one dose of study drug. Patients who do not complete the study, for whatever reason, will have all available data up until the time of termination included in the analysis. For safety analysis presented by study visit, the baseline value will be defined as the last value reported prior to first study drug administration.

7.5.1 *Extent of Exposure*

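### Table 5 footnote c makes patients dosed off-target for manufacturing reasons unevaluable, against Protocol 6.6 and the all-treated denominator stated for the Group 2 CR rate

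*Protocol*

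**What the plan says.** Two protocol passages deal with patients whose dose departs from plan because of manufacturing. Section 6.1, Table 5, footnote c says "these patients will complete the study but will be unevaluable". The footnote is attached to the dose row, which covers Group 1 Arm A, Group 2 and the cohorts. Section 6.6, on lower or higher doses than intended, says "these patients will complete the study but will be evaluable in a separate sub-group".

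Section 9.2, Table 8, and the synopsis cover a related set: patients whose product has fewer cells or misses specification. They "may still be treated, but will be summarized separately from patients whose product meets specifications". The same table entry says that for Group 2 "all efficacy analyses and safety analyses will be conducted in this population", meaning All Treated.

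For the endpoint, Protocol 9.3.3 says that for Subgroup D the "CR rate is defined as the proportion of treated patients who achieve a best response of" CR without minimal residual disease. Subgroup C is worded the same way, with CR also counted. SAP 7.2 defines All Treated with no exception for dose or specification: "Includes all patients who received at least one dose of MT-401 or were randomized to SOC". SAP 7.4.1 adds that "efficacy analyses for Cohorts I-V and Group 2 will be conducted in the all treated patients population". SAP 7.7 reports no change from the protocol.

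If a Cohort III-V regimen is adopted, Protocol 9.1.2 and SAP 7.6 continue Group 2 enrolment to 60 evaluable patients on the final product. Neither document defines *evaluable* as an efficacy set. The only defined set using the word is the DLT-evaluable one, for the lead-in and cohorts.

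**The concern.** For a patient-specific cell product, failing to reach the target dose is something that happens under the treatment strategy. A rule that calls those patients unevaluable removes treated patients on a product-quality criterion and leaves a CR rate for patients whose donor product came out as planned. In Group 2 this is a primary endpoint in an unblinded, single-arm setting, with about 30 patients per subgroup, so a few patients move the estimate.

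In Group 1 the same footnote can act on one arm only. Arm B receives no product and cannot be off-dose. Applying the footnote would remove patients from Arm A on a post-randomisation criterion and leave Arm B untouched.

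It is also unclear whether an off-dose patient fills one of the 30 places in a subgroup, or one of the roughly 10 places that trigger the Group 2 interim review.

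**Working it through.** **1. The passages side by side.**

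| Place | Who is covered | Status |
|---|---|---|
| Protocol Table 5, footnote c | dose differs from that listed because of manufacturing limits | unevaluable |
| Protocol 6.6 | lower or higher dose than intended (manufacturing constraints, or other issues discussed with the sponsor) | evaluable, separate subgroup |
| Protocol Table 8, synopsis | fewer cells, or out of specification | in All Treated, summarised separately |
| Protocol 9.3.3 | Group 2 CR rate | denominator is treated patients |
| SAP 7.2, 7.4.1 | at least one dose | All Treated, used for Group 2 efficacy |

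Rows 1 and 2 cannot both be followed. Row 3 can coexist with rows 4 and 5, since a stratum can be shown separately and still be pooled. It does not say that the headline rate pools it. Row 1 conflicts with rows 4 and 5 if *unevaluable* means left out of the efficacy analysis.

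**2. The plan's own figures.** Protocol Table 7 (SAP Table 3) uses n = 30 and a one-sided exact test at 0.05. The critical count r is the smallest with P(X ≥ r | 30, p0) ≤ 0.05.

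- p0 = 20%: r = 11, since P(X ≥ 11) = 0.0256 and P(X ≥ 10) = 0.061. Power is 81.1% at a true rate of 43% and 90.7% at 47%. The table lists 43% for 80% power and 47% for 90%.
- p0 = 10%: r = 7 (0.0258). Power is 81.0% at 29% and 89.0% at 32%. The table lists 29% and 32%.

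The table's basis is reproduced.

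**3. How far the denominator moves the rate.** Assumptions: 30 treated in a subgroup, 9 CRs among on-target patients, k off-target patients. With them the rate is (9 + c)/30, where c runs from 0 to k. Without them it is 9/(30 − k).

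| k | Included, c = 0 | Included, c = k | Excluded (exact 95% CI) |
|---|---|---|---|
| 3 | 9/30 = 30.0% | 12/30 = 40.0% | 9/27 = 33.3% (16.5 to 54.0) |
| 6 | 9/30 = 30.0% | 15/30 = 50.0% | 9/24 = 37.5% (18.8 to 59.4) |

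Exclusion can raise or lower the rate, depending on whether off-target patients respond less or more often than the others.

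**4. Whether a test could change.** Assumptions: k = 5, no CRs among them, 10 CRs among the other 25, and a 20% historical rate (one row of Table 7).

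- Included: 10/30 = 33.3%, P(X ≥ 10 | 30, 0.20) = 0.061.
- Excluded: 10/25 = 40.0%, P(X ≥ 10 | 25, 0.20) = 0.017.

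The first fails and the second passes at one-sided 0.05. The same holds at 0.025 in the upper tail, the counterpart of the two-sided 0.05 level in SAP 7.4.7.5. With one CR among the five, the included result is 11/30 (p = 0.0256), which passes at one-sided 0.05 and just misses 0.025.

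**The case against.** The strongest reply is that the denominator is already settled. Protocol 9.3.3, Protocol Table 8 and SAP 7.2 and 7.4.1 all use treated patients, and SAP 7.4.7.2 counts patients with no post-baseline assessment as non-responders. The SAP on its own gives one rule. This stands. A reader might infer that the documents support either denominator equally, and they do not. One table footnote is out of line, and one phrase in Table 8 is incomplete.

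The passages also do not cover exactly the same patients. A higher-than-listed dose has no Table 8 rule, and an out-of-specification product at full dose falls outside footnote c. That stands too, and one common rule would close both gaps.

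A reader might take the enrolment target of 60 evaluable patients to mean that off-dose patients are replaced. The text does not go that far. The sentence applies if the Phase 2 regimen is switched, and it replaces patients not treated with the final product. What remains is that nothing says how an individual manufacturing shortfall counts.

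Nor do the documents show that off-target patients are the least likely to respond. They give no response rate by dose received or specification status.

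Finally, the Group 2 objective is estimation, the sample size has no formal power basis, SAP 7.4.7.5 names no null rate, and comparison with the retrospective study is left to a separate SAP. The test in the working is therefore an illustration and not the plan's decision rule.

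Some safeguards exist. SAP 7.1.1 reports Group 1 non-safety outputs by randomised arm. For a dose-based sensitivity set, SAP 7.4.7.6 says "The PP population will exclude patients received less than two-thirds of total planned dose or had other major protocol deviations". But SAP 7.4.1 repeats per-protocol efficacy analyses for Group 1 only, whereas Protocol Table 8 plans them for Group 2 as well.

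**Conclusion.** The concern holds as a conflict between one stated rule and the rest of the plan. Footnote c contradicts Protocol 6.6 directly and is at odds with the all-treated denominator in Protocol 9.3.3 and the SAP. Two things are left unsaid: whether the Table 8 patients are pooled in the headline CR rate, and whether off-dose or out-of-specification patients count toward the 30 per subgroup. It would be too much to say that the primary denominator is undefined, since the SAP defines it.

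The size depends on a frequency that the documents do not give, and 6.6 describes such cases as rare. With 3 of 30 off-target and 9 on-target CRs, the included rate lies between 30% and 40% against 33.3% excluded. With 6 it lies between 30% and 50% against 37.5%. A change in a test result against 20% is possible with whole-number counts (10/30 against 10/25), but it needs 5 off-target patients and no responses among them, both assumed. In Group 1 the footnote would affect Arm A only, although SAP 7.1.1 already points the right way.

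**What to change.** Reconcile the passages around the rule that the SAP already uses:

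- Delete the statement in Table 5 footnote c that these patients are unevaluable.
- In Protocol 6.6, Table 8, the synopsis and SAP 7.2, state once and identically that every patient given any MT-401, of the final Phase 2 product and dose regimen as assigned, is in the primary Group 2 CR denominator and counts toward the 30 in the subgroup. Say that separate summaries are additional to this.
- State in the same places that Group 1 patients are analysed in the arm assigned, whatever product Arm A patients received.
- Add a Group 2 sensitivity analysis restricted to on-target, in-specification patients.
- Define *evaluable* where it governs enrolment, or replace it with the name of a defined set.

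The cost is wording in the protocol and the SAP, best settled before the Group 2 interim review. No new data are needed, and no dose or dosing rule changes. The one drawback is that the headline CR rate may be slightly lower if off-target patients do respond less often.
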